COVER PAGE

Official Study Title: Feasibility of Blood-flow Restriction Training Prehabilitation in Older Adults Awaiting Total Knee Replacement

NCT number: NCT06111690

IRB Approval Date: 09-05-2024

Unique Protocol ID: HSC20210590H

Protocol Template Form

Item 1 UTHSCSA Tracking Number	HSC20210590H
---	--------------

Item 2 Abstract / Project Summary	Provide a succinct and accurate description of the proposed research. State the purpose/aims. Describe concisely the research design and methods for achieving the stated goals. This section should be understandable to all members of the IRB, scientific and non-scientific. DO NOT EXCEED THE SPACE PROVIDED.
--	--

Purpose/Objectives: The overall aim of this research is to demonstrate that preoperative exercises (prehabilitation) using blood-flow restriction training (BFRT) is safe, well tolerated, improves muscle function, decreases functional limitation, and increases physical activity in older adults awaiting total knee replacement (TKR).

Research Design/Plan: This is a single group pre-post design study. Outcomes will be measured at baseline, after 6 weeks of prehabilitation, and 8 weeks after TKR.

Methods: Twenty individuals ≥ 60 years old awaiting TKR due to diagnosis of end-stage knee osteoarthritis who meet the inclusion/exclusion criteria will be invited to participate in a 6 weeks of low-intensity BFRT prehabilitation. We will assess muscle morphology (i.e., cross-sectional area and intramuscular fatty content) using dual x-ray absorptiometry (DEXA) scan, quadriceps muscle strength using an isokinetic dynamometer, a battery of performance-based physical function, self-reported physical function and quality of life, and biomarkers of inflammation using blood serum. Feasibility assessment will be done by looking at safety (i.e., adverse events), compliance, and attrition rate.

Clinical Relevance: The low intensity prehabilitation program using BFRT may lead to improvements in muscle morphology and strength, as well as physical function before TKR. Since muscle weakness and functional limitations experienced preoperatively affect the recovery after TKR, these individuals may experience a significant benefit from our program. Thus, our program may allow patients undergoing TKR to perform daily activities early on postoperatively. Moreover, by increasing physical activity and preventing exacerbation of joint inflammation, our program might impact the general health in older adults after TKR.

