
Item 4
 
Purpose and rationale
 
Insert purpose, objectives and research questions/hypotheses here.
 
If you cut and paste from another document, make sure the excerpted material answers the question
	
Primary outcome: feasibility of BFRT during prehabilitation in older adults awaiting TKR.
 
Secondary outcomes: muscle strength and morphology (i.e., volume and quality), physical function, real-time physical activity and concentration of inflammatory biomarkers.
 
Endpoint: Baseline (T0), after 6 weeks of prehabilitation (T1) and 8 weeks postoperative (T2)
 
Justification for Endpoint: - T0 will provide overall idea on subjects' baseline characteristics of outcome-related data.
 
- T1 will provide data on safety, compliance and attrition rate of the BFRT prehabilitation program, as well as its effect on muscle strength and morphology, physical function, real-time physical activity and concentration of inflammatory biomarkers.
 
- T2 will provide data on the continuing effect of BFRT prehabilitation on muscle strength and morphology, physical function, real-time physical activity and concentration of inflammatory biomarkers postoperatively.
 
Rationale: The low intensity prehabilitation program using BFRT may lead to improvements in muscle morphology and strength, as well as physical function before TKR. Since muscle weakness and functional limitations experienced preoperatively affect the recovery after TKR, this population may experience a significant benefit from our program. Thus, the results of our investigations may allow patients undergoing TKR to perform daily activities early on postoperatively. Moreover, by increasing physical activity and preventing exacerbation of joint inflammation, our program might impact the general health in individuals after TKR.

Item 5 Study Population(s) Being Recruited
 
In your recruitment plan, how many different populations of prospective subjects do you plan to target? Provide number: 1
	
Identify the criteria for inclusion:
	
---	--	--

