Subjects will self-identify as referred by UT Dept. of Orthopaedics provider at least 8 weeks prior to routine total knee replacement surgery. Potential participants will be screened by phone at time of initial reach out to ensure eligibility criteria is met.

Screening. A trained designated tester will conduct a screen interview over the telephone using a structured questionnaire. Then, to validate the inclusion and exclusion criteria obtained by telephone, the tester will conduct an on-site interview using standardized history and physical exam forms. Also, to rule-out peripheral arterial disease, the evaluator will conduct an ankle-brachial index assessment. Only individuals within normal cut-off values for ABI (i.e., between 0.9 and 1.3) will be eligible to participate in the study.

Baseline Assessment (Visit 01). Baseline data will be collected by a trained research assistant. Estimated time to perform the baseline testing is ~2.5 hours. Individuals will be instructed to avoid strenuous physical activity 48hrs prior to testing. Baseline session will be performed in the following sequence: 1) DEXA scan at the Barshop Institute; 2) at the PT laboratory: 2a) blood drawing; 2b) questionnaires on demographics, physical function, quality of life and biomedical information; 2c) performance-based physical function; and 2d) quadriceps muscle strength.

Visit 01 (Baseline; all procedures completed for research)

Informed consent will be obtained by approved research team members and medical history and demographics collected. Falls, Cumulative Illness and Contraindications questionnaires and the mini-mental will be administered by trained staff to confirm inclusion/exclusion criteria. Once all criteria are met, subjects will be asked to complete the following:

Vital signs

- Blood sample will be collected (approx. 30ml) to assess inflammatory biomarkers. Blood samples to analyze concentration of inflammatory biomarkers (research). Blood samples will be stored in the freezers located at the Department of Medical Laboratory Sciences in the School of Health Professions at UTHSCSA. Freezers hold temperature stable at -80oC, which is necessary to maintain the quality of blood samples. A research assistant from the Department of Medical Laboratory Sciences will centrifuge the blood samples to separate serum from plasma. (research)
- Whole-body DXA scan to look at muscle composition of both thighs

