Primary Outcomes: 1) Quadriceps muscle function:

1a. Strength will be measured using an isokinetic dynamometer (Biodex System 4 Pro, Shirley, NY). We will record the quadriceps femoris maximum voluntary isometric contraction (MVIC) as torque output (Nm). Subjects will be seated in the dynamometer's chair with their knee at 60 degrees of flexion. Subject position, stabilization, and gravity correction will be performed according with the Biodex manufacturer's guidelines. Subjects will exert as much isometric force as possible while trying to extend the knee against the force arm of the dynamometer. The MVIC will be the highest torque (Nm) of four trials.³³ Torque will be the variable used in data analysis. Strong verbal encouragement from the tester and visual feedback from the dynamometer screen will be provided during trials. Previous studies using this method in individuals with arthritis indicate that it was tolerated well and did not result in adverse effects.^{34,35}

1b. Cross-sectional area and Quality will be measured using a whole-body DEXA scan to investigate muscle composition of the thigh region bilaterally.^{36,37} Serial axial plane DEXA scan will be used to quantify changes in thigh muscles cross sectional area (CSA) and quality (i.e., amount of intramuscular fat) bilaterally. Subjects will be imaged in supine with the legs extended flat on the table. The scanner measures the absorption of two different energy levels of X-rays as they pass through the body. This information is used to create an image of the body that shows the distribution of bone, fat, and muscle tissue that have different X-ray attenuation. Using these differences in X-ray attenuation, the DEXA software is able to distinguish and quantify the amount of muscle and fat in a specific region of interest, such as the thigh muscles.

Secondary Outcomes:

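### Outcome 1b names thigh muscle cross-sectional area and intramuscular fat, but the scan as described gives only regional amounts of muscle and fat, and no derivation links the two

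*Combined protocol and SAP*

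**What the plan says.** Item 2 (Abstract) ties both morphology variables to one instrument: "We will assess muscle morphology (i.e., cross-sectional area and intramuscular fatty content) using dual x-ray absorptiometry (DEXA) scan".

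Item 4 (Purpose and rationale) lists the outcome among the secondary ones under a different name: "muscle strength and morphology (i.e., volume and quality". Cross-sectional area does not appear there.

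Item 6, Primary Outcomes, places the outcome under a quadriceps muscle function heading, beside dynamometer strength (1a). Item 1b says: "Cross-sectional area and Quality will be measured using a whole-body DEXA scan to investigate muscle composition of the thigh region bilaterally". It then describes the acquisition: "Serial axial plane DEXA scan will be used to quantify changes in thigh muscles cross sectional area (CSA) and quality", and defines the second variable as "quality (i.e., amount of intramuscular fat) bilaterally". The same paragraph explains the physics (absorption of X-rays at two energies as they pass through a supine subject) and the output: "the DEXA software is able to distinguish and quantify the amount of muscle and fat in a specific region of interest".

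Under Study visit procedures, Visit 01 has "Whole-body DXA scan to look at muscle composition of both thighs". Visit 08 has a whole-body DEXA scan, and Visit 10 repeats the Visit 08 procedures.

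Under Statistical Considerations, Statistical Analyses, morphology is one of the secondary outcomes compared between T0-T1, T0-T2 and T1-T2 by the Wilcoxon signed-rank test.

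**The concern.** An axial cross-sectional area is measured on a slice across the limb. Intramuscular fat is the fat lying within muscle, as distinct from the fat over and around it. The measurement described in 1b is a transmission image with a total for each tissue in a chosen region. A regional total is neither an area nor a volume, and it does not say where in the thigh the fat lies.

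If the names stay, a change in total thigh fat would be reported as a change in muscle quality, and a change in thigh lean tissue as a change in cross-sectional area. A real change in intramuscular fat could be hidden by the larger fat compartment, and a change in subcutaneous fat could be read as a training effect on muscle.

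**Working it through.** The plan gives no effect size, standard deviation, power or measurement error for either variable, so there is no figure to reproduce. The check sets the named outcomes against the described output.

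**1. Named against measured**

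| Named outcome | Where | What 1b says the software returns | Stated link |
|---|---|---|---|
| Muscle cross-sectional area | Item 2; Item 6, 1b | Amount of muscle in a region | None |
| Muscle volume | Item 4 | Amount of muscle in a region | None |
| Intramuscular fat (quality) | Item 2; Item 6, 1b | Amount of fat in a region | None |

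**2. Could another instrument supply the values?** Visits 01, 08 and 10 schedule whole-body DEXA only. No CT, MRI or ultrasound appears.

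**3. Could area be derived?** The most that regional lean mass allows is a mean area:

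mean area = lean mass / (density × region length)

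The plan gives no density, no region length, no region borders and no such formula. The result would also cover all lean tissue in the thigh region.

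**4. Could intramuscular fat be recovered from regional fat?** Illustration with assumed values (none is in the documents): regional thigh fat 4.0 kg, intramuscular share 5% to 20%.

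- Intramuscular fat: 0.05 × 4.0 = 0.2 kg, up to 0.20 × 4.0 = 0.8 kg. The regional reading is 4.0 kg in both cases, so the reading does not identify the share.
- A 10% relative change in intramuscular fat is 0.02 kg to 0.08 kg. In the regional reading that is 0.02 / 4.0 = 0.5% to 0.08 / 4.0 = 2%.
- The other thigh fat is 3.8 kg to 3.2 kg. A change in it of 0.02 / 3.8 = 0.5% to 0.08 / 3.2 = 2.5% gives exactly the same reading with no change in intramuscular fat.

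The 4.0 kg cancels in these percentages; only the assumed share matters.

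**5. Where the values go.** They enter three paired comparisons, T0-T1, T0-T2 and T1-T2. All three carry the naming problem, because the same scan is used at each visit.

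**The case against.** The strongest reply is that 1b never says its image is flat, lacks slices or cannot separate fat compartments. Those limits are general knowledge of the technique. The two references cited for the method cannot be seen here and may describe a DEXA-derived surrogate for area or muscle fat. This stands in part. A reader might infer that no valid value could exist at any visit. The documents support less: the described output is a regional amount, and no derivation from it is stated. If a surrogate is intended, the plan neither names it nor gives its formula.

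Other stronger readings also go beyond the text:

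- **Thigh lean mass passed off as quadriceps size.** Only the umbrella heading says quadriceps. Item 1b itself speaks of thigh muscles, and Visit 01 of both thighs.
- **A later trial planned on the wrong variable.** The Data Analysis Plan says its change values will inform sample size for a larger trial, but its outcome list leaves morphology out.
- **An implant artefact in the T0-T2 change.** This arises only in the operated limb at T2, and only if the region reaches the knee. The documents give no region border and say nothing on how metal is handled.
- **A large count of wrong measurements.** 20 subjects × 2 thighs × 3 visits = 120 thigh-visits, with full retention. That is a count of scans, not a measure of bias.

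**Conclusion.** The concern holds as a fault in the definition and labelling of outcome 1b. It is more than missing detail: followed literally, the plan tests one quantity and reports another. It affects both morphology variables in all three comparisons.

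Its numerical size cannot be had from the documents; the 0.5% to 2% range rests wholly on the assumed 5% to 20% share. The conclusion rests on the plan's own account of the scanner output, the absence of other imaging in the schedule, and the absence of any stated conversion. A referenced surrogate, written into the plan and labelled as such, would change it.

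The reach is limited. Item 4 makes feasibility the primary outcome and morphology secondary, and Statistical Analyses also treats morphology as secondary; only the heading above 1b calls it primary. Conclusions on safety, compliance and retention do not use the scan, and strength comes from the dynamometer.

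**What to change.** 1. In Item 2, Item 4, Item 6 (1b) and Statistical Considerations, define morphology once, as DEXA thigh lean mass and thigh fat mass (or percent fat), per limb.
2. Delete the references to serial axial imaging, cross-sectional area, volume and intramuscular fat in describing this outcome. The exception is a specified, referenced DEXA-derived surrogate; in that case give its formula and call it a surrogate wherever it is reported.
3. Fix one region of interest with the same landmarks at T0, T1 and T2 and its lower border above the implant site. This guards against a region that may not be comparable at T2 in the operated limb.
4. Report surgical and non-surgical limbs separately.

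The cost is wording and a region rule applied to scans already planned; visits and sample size do not change. The sponsor gives up the muscle-quality claim or relabels it as a surrogate.

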
Older adults with knee osteoarthritis awaiting total knee replacement
	
Individuals will be included if they: (a) are awaiting primary unilateral TKR due to diagnosis of end-stage KOA. Potential individuals must have at least 8 weeks waiting time in between study baseline assessment and surgery. This 8-week timeframe will allow for completion of baseline (T0) and follow-up assessments (T1: immediately after 6-week prehabilitation program); (b) are older than 60 years; (c) speak fluent English to reliably complete the study questionnaires and understand study instructions.
	
To ensure safety, Individuals will be excluded from the study if they: (a) have a history of cardiovascular disease, uncontrolled hypertension (blood pressure $\geq 140/90$ mmHg), deep-vein thrombosis, varicose veins, or rhabdomyolysis; (b) have absolute contraindications to exercise, as established by the American College of Sports Medicine (uncontrolled arrhythmias, third degree heart block, recent EKG changes, unstable angina, acute myocardial infarction, and acute congestive heart failure); (c) report of 2 or more falls within the past year; (d) cannot walk a distance of 100 feet (30.5 meters) without an assistive device or need of a rest period; (e) have bilateral TKR or undergoing TKR revision or other total joint replacement in the lower extremities; or (f) have severe visual or hearing impairment. In addition to the affects that these impairments have on safety during participation in the intervention, they may also interfere with data collection (questionnaires and telephone checks); (g) have a lower extremity amputation; (h) are unable to comfortably bear weight on the affected knee; (i) have a BMI above 40. This exclusion is used because subjects with BMI ≥ 40 are more likely to develop patellar radiolucencies, have poorer muscle function and more pain.
 
To minimize potential confounding effects, individuals will be excluded if they have: (j) history of muscular disease (e.g., muscular dystrophy) or neurological disorder that may affect lower extremity function (e.g., cerebrovascular accident, neuropathy, Parkinson's disease, multiple sclerosis); (k) had additional surgery to the lower extremities within the past 12 months.

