- Physical Functional Assessment to include self-selected gait speed, timed 5 chair rise, single leg stance time, timed-up and go test, stair ascend/descend test, and 6-minute walk test
- Patient-Reported Outcomes Measurement (PROMIS)
- RAND-36-item Health Quality of Life Survey
- Subjects will be provided with an actigraph monitor device and asked to wear it for one-week to assess a baseline physical activity prior to BFRT sessions

Visit 02 – Visit 07 (Treatment Weeks 1 through Week 6; all procedures completed for research)

One week after baseline visit, subjects will complete 12-18 sessions of low-intensity blood flow restriction training (BFRT), two to three times a week, for six weeks, based on patient willingness/availability. A minimum of 12 sessions is required for study participation. BFRT sessions will be completed as described above at the UT Physical Therapy Research Lab. An exercise and pain log will be completed during and after each intervention session. All training sessions will be provided by qualified providers who are also IRB approved research team members.

Visit 08 (Pre-operative Follow up Week 7; all procedures completed for research)

A pre-operative follow-up visit will be scheduled one week after completion of BFRT intervention sessions. Subjects will be asked to complete the following:

Vital signs

Blood sample will be collected (approx. 30ml) to assess inflammatory biomarkers (research).

Whole-body DEXA scan (research)

Physical Functional Assessment to include self-selected gait speed, timed 5 chair rise, single leg stance time, timed-up and go test, stair ascend/descend test, and 6-minute walk test

Patient-Reported Outcomes Measurement (PROMIS)

RAND-36-item Health Quality of Life Survey

Actigraph monitor provided at the end of Treatment week 6 and collected at time of pre-op follow up Week 7

Visit 09 - Routine Total Knee Replacement Surgery (Routine Standard of Care)

Routine knee surgery will be performed per standard of care. Results will be requested for research purposes

Visit 10 (Post-operative Follow up 8-weeks after TKR surgery; all procedures completed for research)

Same procedures as V08 will be completed

Visit 11 – this is a virtual research visit only. Subjects will be asked to mail actigraph monitoring device by mail in a prepaid envelope provided by the study team. This will qualify as the end of study visit.

Adverse events will be monitored at each visit.

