biomarkers. The laboratory will use the 'MILLIPLEX® MAP Human High Sensitivity T Cell Magnetic Bead Panel' to assess a panel of 8 inflammatory biomarkers: Interleukin (IL)-1 β , IL-2, IL-5, IL-6, IL-10, IL-12p70, IL-13 and Interferon- γ .^{32,53}

Additional Measures

1) Demographic factors: age, gender, ethnicity, marital and educational status

2) Biomedical factors

a) Medication prescribed and over-the-counter used for pain will be recorded in the medication form. We will record the current and highest dosage of any pain medication used during the last month (when performing pre-intervention evaluation), or during the interval between evaluations.

b) Comorbidity data will be collected using the Cumulative Illness Rating Scale.⁵⁴

c) Body Mass Index will be calculated as the subject's body weight divided by the height squared.

d) Knee Range of Motion will be measured in the supine position utilizing a standard goniometer. The available range of knee flexion and extension will be measured. When measuring passive knee extension, the heel will be elevated on a bolster to ensure the end range of extension is achieved.

e) Knee Pain in both knees (surgical and non-surgical sides) will be measured using an 11-point (0 to 10) numeric scale. The scale will be anchored at one end with the phrase "no pain" (0) and at the other end with the phrase "worst imaginable pain". Subject will be instructed to report the greatest pain during last 24h.^{55,56}

Research personnel will keep track of assessment procedures using a checklist. An exercise log will be used to track delivered exercise sessions. All questionnaires will be self-administered using Redcap.

Although subjects are asked to not participate in any exercise-related program during the study period, research personnel will track exercises performed by subjects on a log.

Study personnel reserve the rights to discontinue delivery of intervention if subject presents with muscle or joint pain that cannot be resolved by administering over-the-counter pain medication.

Research personnel will ensure to follow-up with subjects who have discontinued the study in regards to their recovery from muscle or joint flare-ups due to study intervention to monitor AE, SAE and/or UPIRSOs.

Statistical Considerations

Statistical Hypotheses

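### The safety conditions set at entry are not re-checked during the 12–18 cuffed sessions, and the written stopping ground and adverse-event summary centre on pain, so the safety hypothesis is weakly tested for the risks the protocol itself names

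*Combined protocol and SAP*

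**What the plan says.** **Entry.** Item 5 introduces its first group of exclusions with the words "To ensure safety, Individuals will be excluded from the study if they". Criterion (a) covers those who "have a history of cardiovascular disease, uncontrolled hypertension" (defined there as 140/90 mmHg or above), "deep-vein thrombosis, varicose veins, or rhabdomyolysis"; criterion (b) adds acute cardiac conditions. Sickle cell disease, cuff placement on a limb with lymphedema or vascular access, and any current medical emergency are printed at the end of the list, outside the safety group.

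**When the criteria are checked.** Item 6, Study visit procedures, describes a telephone screen, after which "to validate the inclusion and exclusion criteria obtained by telephone, the tester will conduct an on-site interview using standardized history and physical exam forms", together with an ankle-brachial index. At Visit 01, "Falls, Cumulative Illness and Contraindications questionnaires and the mini-mental will be administered by trained staff to confirm inclusion/exclusion criteria".

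**During training.** Vital signs are listed for Visit 01, for Visit 08 and, by cross-reference to Visit 08, for Visit 10. They are not listed for Visits 02–07, where the entry reads "An exercise and pain log will be completed during and after each intervention session". The same section says that sessions are given by qualified, IRB-approved team members and that adverse events are monitored at every visit. The Step-by-Step Methods start the cuff at 50% of full-occlusion pressure and raise it by 5–10% once a week, up to 80%, as tolerated.

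**Stopping and follow-up.** Under Additional Measures: "Study personnel reserve the rights to discontinue delivery of intervention if subject presents with muscle or joint pain that cannot be resolved by" over-the-counter analgesia. Those who discontinue are followed "in regards to their recovery from muscle or joint flare-ups due to study intervention"; the sentence then gives the purpose as monitoring AEs, SAEs and UPIRSOs.

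**Analysis.** The Statistical Hypotheses include that the exercise protocol is safe. The Statistical Analyses section promises descriptive statistics on adverse events during sessions and at each timepoint, and explains the term in brackets, introduced by i.e., as pain in joints or muscles.

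**The concern.** Several of the entry conditions are states that can change over a few weeks, blood pressure most obviously. The protocol treats them as important enough to bar someone from cuffed exercise, yet it does not say how they would be recognised, or what would follow, if they arose while the cuffs are in use.

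Two things are at stake. The first is participant protection during the period when cuff pressure is being increased. The second is inference. Item 4 makes feasibility the primary outcome and Item 2 counts safety as part of it. If the session record, the stopping ground and the adverse-event summary all centre on musculoskeletal pain, a favourable safety result says little about the vascular, cardiac and muscle-breakdown risks that the protocol itself lists.

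**Working it through.** **Inputs.** 20 participants (Sample Size Determination); two to three sessions a week for six weeks (Visits 02–07); training starts one week after baseline (Visits 02–07); Visit 08 is one week after the last session. I assume that vital signs include blood pressure.

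1. *Sessions per participant.* 2 × 6 = 12 and 3 × 6 = 18. This reproduces the stated 12–18.
2. *Sessions in the trial, if all 20 complete.* 20 × 12 = 240; 20 × 18 = 360. Dropout would lower these totals.
3. *Sessions with scheduled vital signs.* 0 of 240–360.
4. *Interval between scheduled readings, Visit 01 to Visit 08.* 1 week before training + 6 weeks of training + 1 week after = about 8 weeks.
5. *Sessions per numbered training visit.* Visits 02–07 are six visits, so 12 / 6 = 2 to 18 / 6 = 3 sessions each. Monitoring adverse events at each visit need not mean at each session, although the Statistical Analyses section does foresee adverse-event data from sessions.

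**The text side by side.**

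| Situation arising during training | Scheduled measurement | Stated action |
|---|---|---|
| Blood pressure reaches 140/90 without symptoms | None until Visit 08 | None |
| Symptomatic vascular, cardiac or muscle-breakdown event | General adverse-event monitoring; staff present | None specified |
| Lymphedema or vascular access on the limb | None listed, though the criterion's wording could apply each time a cuff is fitted | None specified |
| Muscle or joint pain | Exercise and pain log | Discretionary stop if not resolved by over-the-counter medication |

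Only the last row has both a dedicated record and a stated consequence. It overlaps with one safety exclusion, criterion (h) on comfortable weight-bearing through the affected knee, but not with criteria (a) or (b).

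**The case against.** The strongest reply is that the protocol is not silent on safety during training. Adverse events are monitored at each visit, qualified team members give every session, cuff progression depends on tolerance, and entry screening has several layers. This stands, and it rules out one tempting inference: that the trial would report on safety without having looked. A symptomatic event could well be noticed. What the reply does not supply is a measurement for a symptomless change or an action once something is noticed.

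A reader might also infer that someone who comes to meet a safety exclusion would be kept in training. The documents do not say so. Reserving a right to stop on one ground does not exclude stopping on others, and the gap is one of silence, not instruction. Nor is it right that pain is wholly separate from the safety exclusions, given criterion (h).

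A third inference would be that events other than flare-ups go unfollowed after discontinuation. The full sentence names AEs, SAEs and UPIRSOs. Its scope is ambiguous because it is tied to recovery from flare-ups, but it does not limit follow-up to them.

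Finally, Item 7 refers risks to the informed consent document, which was not available for this review. Withdrawal or stopping language may be there, so the point is limited to the protocol text. The documents also give no rate at which participants would cross an entry threshold, so the counts above measure unmonitored exposure, not expected harm.

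**Conclusion.** The point holds in limited form. In the protocol text, safety conditions that can newly arise are checked at screening and Visit 01 only. None of the 240–360 cuffed sessions (all 20 completing) has scheduled vital signs, and about 8 weeks separate scheduled readings. Adverse-event monitoring exists but has no action attached, the only stated stopping ground is unresolved muscle or joint pain, and the analysis describes adverse events in the same terms. The safety hypothesis is therefore weakly tested for the named non-pain risks.

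This rests on the visit lists being complete as written and on no further rule standing in the consent document. Severity is should-fix: there is no evidence of likely harm, but the gap touches participant protection and part of the primary feasibility claim.

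**What to change.** Reconcile the Item 5 exclusions with the Step-by-Step Methods, the Visit 02–07 entry, the discontinuation text under Additional Measures, and the Statistical Analyses section. Specifically:

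- Record on the existing session log whether the protocol's own entry safety conditions, including blood pressure, still hold. Name the items printed at the end of the exclusion list explicitly, since they fall outside the safety group.
- State which role documents the decision when a condition no longer holds. Thresholds and actions are for the investigators to set.
- State whether adverse-event monitoring takes place at every session or once per numbered visit.
- Report all adverse events in the safety summary, not only joint or muscle pain.
- Reword the follow-up sentence so that AE, SAE and UPIRSO follow-up is clearly not limited to flare-ups.

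The cost is a protocol amendment, a short addition to an existing form and a few minutes per session. Reported compliance may fall slightly if some sessions are held.
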